---

**COMPLIANCE STATEMENT:**

This clinical investigation will be conducted in accordance with this Clinical Investigation Plan (CIP), the Declaration of Helsinki and the applicable regulatory requirements (US 21 CFR Part 50, 21 CFR Part 56, 21 CFR Part 54, and 21 CFR Part 11, etc., and OUS ISO 14155:2020 standard and the appropriate local legislation(s)). The most stringent requirements, guidelines or regulations must always be followed. The conduct of the clinical investigation will be approved by the Food and Drug Administration (FDA) and the appropriate Institutional Review Board (IRB) or Ethics Committee (EC) of the respective investigational site, and as specified by local regulations.

## 1.0 INTRODUCTION

The XIENCE Skypoint Large Vessel Post-Approval Study (PAS) (called “SPIRIT XLV PAS” hereafter) is a prospective, single-arm, open-label, multi-center global (United States [US] and outside of US [OUS]) clinical study to evaluate the continued safety and effectiveness of the XIENCE Skypoint Large Vessel (LV) sizes (stent diameters 4.5 mm and 5.0 mm in stent lengths of 12-33 mm) everolimus-eluting coronary stent system (EECSS) after the US market approval, in a minimum of [REDACTED], with a minimum of [REDACTED].

[REDACTED] This clinical study will be conducted in accordance with this clinical investigation plan (CIP). All investigators involved in the clinical study will be qualified by education, training, or experience to perform their tasks and this training will be documented appropriately.

## 1.1 Background and Rationale

### 1.1.1 Background

A post-approval study to evaluate the continued safety and effectiveness of the XIENCE Skypoint stent diameters 4.5 and 5.0 mm was required by FDA, which is planned to be conducted following the clinical investigation plan (CIP) described in this document.

- 
- i -XIENCE PRIME Everolimus Eluting Coronary Stent System (XIENCE PRIME): P110019, approved 11/1/11  
-XIENCE Xpedition Everolimus Eluting Coronary Stent System (XIENCE Xpedition): P110019 / S025, approved 12/21/12  
-XIENCE Alpine Everolimus Eluting Coronary Stent System (XIENCE Alpine): P110019 / S070, approved 9/3/14  
-XIENCE Sierra Everolimus Eluting Coronary Stent System (XIENCE Sierra): P110019 / S094 approved 5/22/18  
-XIENCE Skypoint Everolimus Eluting Coronary Stent System (XIENCE Skypoint): P110019 / S113 approved 5/13/21  
ii - MULTI-LINK VISION® (VISION): P020047, approved 7/16/ 3 - MULTI-LINK MINI-VISION® (MINI-VISION): P020047/S003, approved 9/10/04  
- Multi-Link 8® and Multi-Link 8® Long Lesion Coronary Stent System (ML8): P020047/S017, approved 6/22/10  
- Multi-Link 8® Small Vessel Coronary Stent System (ML8): P020047/S022, approved 8/31/10

### 1.1.2 Rationale for Conducting this Clinical Study

The diameters of the coronary arteries have been suggested to be a potential predictor of coronary artery disease (CAD) occurrence and severity. Several previous investigations have examined the influence of vessel diameter on adverse event rates over time. Both Hsieh *et al.* and van der Heijden *et al.* found that small vessel lesions (< 2.5 mm) had similar or higher adverse event rates than larger vessel lesions (> 3.0 mm). Although expected to be safe, the currently commercially available drug eluting stents (DES) with large diameters (4.5 mm and above) in the US and globally are limited, resulting in limited choices for physicians to treat large coronary artery lesions.

Prior to the market approval of the XIENCE Skypoint stent diameters 4.5 and 5.0 mm in the US, the XIENCE Family of Stents were commercially available in sizes up to 4.0 mm in diameter, which can treat vessels up to 4.25 mm reference vessel diameter (RVD) with a maximum of 5.50 mm post dilatation expansion diameter. The new XIENCE Skypoint stent diameters 4.5 and 5.0 mm have expansion capabilities to treat vessels up to 5.25 mm RVD with an increased maximum post-dilatation expansion diameter up to 5.75 mm, compared to 5.50 mm for XIENCE Sierra, and without any modification to the stent design or manufacturing process. Owing to the similar design of the XIENCE Skypoint stent diameters 4.5 and 5.0 mm to the other XIENCE Family of Stents, clinical evidence from previous Abbott sponsored clinical trials for the XIENCE Family of Stents relevant to large vessel treatment applies to the XIENCE Skypoint stent diameters 4.5 and 5.0 mm.

The XIENCE V USA clinical trial was a real-world post-market study of the XIENCE V stent that enrolled over 8,000 subjects, of which 5,020 were followed up through 4 years. To understand the safety and effectiveness of the XIENCE Skypoint stent diameters 4.5 and 5.0 mm, data from the XIENCE V USA clinical trial were analyzed to evaluate the clinical results between subjects receiving larger stents to treat a target lesion RVD  $\geq 4.0$  mm to those receiving smaller stents to treat target lesion RVD < 4.0 mmvi. Overall, risk factors were similar between the  $\geq 4.0$  mm and < 4.0 mm groups, but the  $\geq 4.0$  mm group had a higher proportion of lesions located in the left main coronary artery (LMCA) (6.4% vs 1.0%) and vessel grafts (15.9% vs 4.7%) compared to the < 4.0 mm group. This finding is an important characteristic as lesion location in the LMCA or graft is a known risk factor for target lesion revascularization (TLR). Additionally, no differences were observed in target lesion failure (TLF) rate through 1 year between the  $\geq 4.0$  mm and < 4.0 mm groups and the TLF rates remained comparable over 4 years.ii To further support the XIENCE V USA trial analyses, the SPIRIT IV (a pre-approval study for XIENCE V) and SPIRIT PRIME (a pre-approval study for XIENCE PRIME) trial data were used to perform a regression analysis comparing vessel RVD to TLF and stent thrombosis (ST) event rates. The regression analysis found no significant increases in TLF or ST event rates as the size of the treated

iii Data on file at Abbott. The 15 million implants is based on DES data through Q1, 2020

vessel increases. Collectively, the results demonstrate that treatment with the 4.5 and 5.0 mm diameter stents in the treatment of RVD  $\leq 5.25$  mm is expected to be safe and will have comparable outcomes to vessels treated with smaller stents. The clinical evidence led to the commercial approval of the XIENCE Skypoint stent diameters 4.5 and 5.0 mm in the treatment of large coronary vessels without a pre-market study.

The SPIRIT XLV PAS is conducted to evaluate the continued safety and effectiveness of the XIENCE Skypoint stent diameters 4.5 and 5.0 mm in a real-world setting.

## **2.0 CLINICAL STUDY OVERVIEW**

### **2.1 Clinical Study Objective**

To evaluate the continued safety and effectiveness of the XIENCE Skypoint stent diameters 4.5 and 5.0 mm in stent lengths of 12-33 mm during commercial use in a real-world setting.

### **2.2 Device(s) Used in the Clinical Study**

Commercially approved XIENCE Skypoint Everolimus Eluting Coronary Stent System (EECSS) stent diameters 4.5 and 5.0 mm.

- Stent diameters: 4.5 mm, 5.0 mm
- Stent lengths: 12, 15, 18, 23, 28 and 33 mm

#### **2.2.1 Indication for Use/Intended Purpose**

Per US Instructions For Use (IFU), the XIENCE Skypoint stent system is indicated for improving coronary artery luminal diameter in patients, including those at high risk for bleeding and those with diabetes mellitus, with symptomatic heart disease due to *de novo* native coronary artery lesions (length  $\leq 32$  mm) with reference vessel diameters of  $\geq 2.25$  mm to  $\leq 5.25$  mm. In addition, the XIENCE Skypoint stent system is indicated for treating *de novo* chronic total coronary occlusions. For OUS geographies, please refer to the approved country specific indication for use. The indications for XIENCE can be found in the IFU provided with the product or on the Abbott website <https://vascular.eifu.abbott>.

#### **2.2.2 Description of the Device(s) Under Investigation**

XIENCE Skypoint stents are composed of a L-605 cobalt chromium (CoCr) and coated with poly (n-butyl methacrylate) (PBMA) and copolymer of vinylidene fluoride and hexafluoropropylene (PVDF-HFP)/everolimus pre-mounted on a balloon catheter delivery system. The stent designs, stent size matrix, active pharmaceutical ingredient (everolimus), drug dose density, primer and drug eluting layer coating formulations, manufacturing process for incorporating the drug (drug/polymer solution compounding and solution spray coating process), sterilization process, stent contacting material and container closure system materials of XIENCE Skypoint stent diameters 4.5 and 5.0 mm are identical to those of XIENCE Sierra. The recipe parameters for drug spray passes use a narrower range of drug spray passes (60-80) compared to 40-80 for the XIENCE Family of Stents to achieve the same coating performance to the same specifications. The narrower range of drug spray passes is within the existing spray passes for the XIENCE family of stents, which doesn't impact the clinical justification presented in this section. The post-dilatation expansion diameter of the medium stent design of XIENCE Skypoint is

increased to 5.75 mm compared to 5.5 mm for the medium stent design of XIENCE Sierra to offer greater post-dilatation capability, which does not require any modification to the stent design or manufacturing process.

The XIENCE Skypoint delivery catheter uses the same deployment processes as other Abbott Rapid Exchange (RX) stent systems. All materials, including colorants, used in the XIENCE Skypoint delivery system have been used in the XIENCE family of catheters and were previously tested for biocompatibility.

The XIENCE Skypoint delivery system is based on the XIENCE Sierra delivery system. The XIENCE Skypoint balloon is similar to XIENCE Sierra as it uses the same single blow balloon methodology and material (i.e., a single layer of Pebax 72D). The XIENCE Skypoint stent diameters 4.5 and 5.0 mm balloon extrusion and tooling have been modified to facilitate the larger balloon sizes (i.e., 4.5 and 5.0 mm). The XIENCE Skypoint delivery system shaft/catheter utilizes a single-layer Pebax 72D outer member material identical to XIENCE Sierra and is manufactured using the same hot die technology as the XIENCE Sierra outer member. There is a dimensional change in the outer member between XIENCE Skypoint and XIENCE Sierra. The XIENCE Skypoint medium stent outer member has one (1) continuous diameter (single necked). The XIENCE Skypoint stent diameters 4.5 and 5.0 mm outer member has two (2) different diameters (dual necked) similar to the XIENCE Sierra outer member (dual necked). In comparison to XIENCE Skypoint medium stents and XIENCE Sierra catheter shaft design, the XIENCE Skypoint stent diameters 4.5 and 5.0 mm catheter shaft design has been modified:

- inner diameter of the outer member is increased to maintain balloon deflation performance to the same specifications as XIENCE Sierra
- outer diameter of the outer member is increased to maintain catheter tensile strength to the same specifications as XIENCE Sierra.

The dimensional change to the outer member of the delivery system shaft is not considered to impact clinical outcomes and has been assessed through non-clinical testing.

### **3.0 CLINICAL STUDY DESIGN**

The SPIRIT XLV PAS is a prospective, single-arm, multi-center, US and OUS post-approval observational study in a [REDACTED] to evaluate the continued safety and effectiveness of the XIENCE Skypoint stent diameters 4.5 and 5.0 mm in the treatment of *de novo* native coronary artery lesions.

#### **3.1 Clinical Study Procedures and Follow-up Schedule**

[figure not shown]
A minimum of [REDACTED] will be registered in the SPIRIT XLV PAS. [REDACTED]

Each subject will be followed for three years. All subjects will have a follow-up visit at 30 days, 6 months, 1 year, 2 years and 3 years. All follow-ups must be conducted directly with the subject and can be either a clinic visit or a phone visit. Refer to the detailed follow-up schedule in **Section 6.4.4**.

Note: If the scheduled visit occurs outside the allowed window, it is not considered a missed visit/contact. It is a protocol deviation but will still be considered a completed visit.

The study procedures, data collection and follow-up requirements of this clinical study are described in Figure 1 below.

**Figure 1 Clinical Study Flowchart**

Note: Protocol Deviation is further explained in Section 10.6

### 3.2 Measures Taken to Avoid and Minimize Bias

A Clinical Events Committee (CEC) and an angiographic core laboratory will be utilized on this study to avoid and minimize bias.

### 3.2.1 Clinical Event Committee

A CEC will review and adjudicate all clinical endpoint events, and also determine the relationship to the investigational device XIENCE Skypoint stent diameters 4.5 and 5.0 mm. [REDACTED]

### 3.2.2 Angiographic Core Lab

The angiographic core lab will receive and review baseline images from index procedure (i.e., pre- and post-procedure) to ensure quality and readability of the images. [REDACTED]

## 3.3 Suspension or Early Termination of the Clinical Study

## 4.0 ENDPOINTS

### 4.1 Primary Endpoint iv

The descriptive primary endpoint is Target Lesion Failure (TLF) at 1 year. iv

- TLF is defined as the composite of cardiac death (CD), myocardial infarction (MI) related to the target vessel (TV-MI), or ischemic driven target lesion revascularization (ID-TLR).
- For the assessment of periprocedural MI, modified Academic Research Consortium (ARC) II definition will be used. Cardiac troponin (cTn) will be used for the primary cardiac biomarker for MI assessment. For the assessment of spontaneous MI, the 4th universal MI definition will be used. Both MI definitions are defined in **Appendix II**.

**Note:**

### 4.2 Secondary Endpoint

The descriptive secondary endpoints are defined as:

1. Target lesion failure (TLFsp-MI) at 1 year iv
  - TLFsp-MI is defined as the composite of CD and TV-MI, including spontaneous MI and excluding periprocedural MI and, or ID-TLR.
  - cTn will be used for the cardiac biomarker for MI assessment. For the assessment of spontaneous MI, the 4th universal MI definition will be used.
2. Target Lesion Failure (TLFSCAI) at 1 year iv
  - TLFSCAI is defined as the composite of CD and TV-MI, including both periprocedural MI and spontaneous MI, or ID-TLR.
  - For the assessment of periprocedural MI, Society for Cardiovascular Angiography and Intervention (SCAI) definition will be used, and cTniv will be used for the primary cardiac biomarker for MI

iv [REDACTED]  
da [REDACTED]  
v [REDACTED]  
[REDACTED]  
[REDACTED]  
[REDACTED]

assessment. For the assessment of spontaneous MI, the 4th universal MI definition will be used. Both MI definitions are defined in **Appendix II**.

### 4.3 Other Endpoints

Clinical outcomes will be evaluated at each follow-up time point.

#### Composite Outcomes

#### Individual Clinical Outcomes

## **5.0 SUBJECT SELECTION AND WITHDRAWAL**

### **5.1 Subject Population**

This clinical study will register subjects of all genders from the general population 18 years or older. A minimum of [REDACTED] will be registered in the study.

Subjects in which the LMCA contains the target lesion can be treated but are not to exceed [REDACTED] of the study population.

### **5.2 Subject Recruitment/Screening and Informed Consent**

#### **5.2.1 Subject Recruitment and Screening**

A member of the site's clinical study team previously trained in the CIP must evaluate subjects for the general clinical study eligibility criteria. A subject who does not satisfy all general eligibility criteria prior to informed consent is considered a screen failure and should not be registered in the clinical study. Subjects who sign informed consent, have at least one study device implanted, and are later determined to not meet the inclusion/exclusion criteria prior to discharge will be withdrawn from the study, and considered screen failures. Then, sites will ask the subjects to sign an Informed Consent form following the established Informed Consent process (described in **Section 5.2.2**) if they wish to participate in the clinical study.

#### **5.2.2 Informed Consent**

An informed consent form (ICF) must be obtained from a subject who is willing to participate in the SPIRIT XLV PAS study prior to discharge. The subject's consent has to be prior to any study-specific procedures, if not the site's SOC. These may include pre- and post-procedure cardiac biomarker collections, and SYNTAX score  $\leq 22$  (per site assessment) if LMCA is the target vessel. The investigator or his/her authorized designee (if applicable) will conduct the informed consent process, as required by applicable regulations and the center's IRB/EC. This process will include a verbal discussion with the subject on all aspects of the clinical study relevant to the subject's decision to participate, such as details of clinical study procedures, anticipated benefits, and potential risks of clinical study participation. Sites must inform subjects about their right to withdraw from the clinical study at any time and for any reason without sanction, penalty, or loss of benefits to which the subject is otherwise entitled. Withdrawal from the clinical study will not jeopardize their future medical care or relationship with the investigator.

During the discussion, the Principal Investigator or his/her authorized designee will avoid any improper influence on the subject and will respect subject's legal rights. Financial incentives will not be given to the subjects. Subjects may be compensated for time and travel directly related to their participation in the clinical study. The site shall provide the subject with the ICF written in a language that is understandable to the subject and that has been approved by the center's IRB/EC. The subject shall have adequate time to review, ask questions, and consider participation. The Principal Investigator or his/her authorized designee will make efforts to ensure that the subject understands the information provided. If the subject agrees to participate, he/she must sign and date the ICF, along with the person obtaining the consent

prior to any study-specific requirements. The dated signatures can be electronic. The site will file the signed original in the subject's hospital or research charts and provide a copy to the subject. The site will follow local hospital and EC/IRB provisions for documenting electronic ICF signature.

Sites should report any failure to obtain informed consent from a subject to the Sponsor [REDACTED] and to the reviewing center's IRB/EC according to the IRB's/ EC's reporting requirements.

During the clinical study, if new information becomes available that can significantly affect a subject's future health and medical care, the Principal Investigator or his/her authorized designee (if applicable) will provide this information to the subject. If relevant, sites will ask the subject to confirm their continuing informed consent in writing.

For live cases at congresses, the subject must sign a specific Live Case ICF, approved by the IRB/EC. The investigator must notify the Sponsor prior to performing a live case.

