### 5.4 Subject Enrollment and Registration

A subject is considered to be enrolled in the study from the moment the subject provides written informed consent. A subject is considered to be registered in the study when the subject provides written informed consent, has at least one XIENCE Skypoint stent diameters 4.5 and 5.0 mm implanted, and is confirmed to meet all general/angiographic eligibility criteria.

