## **6.4 Discharge Plan**

Discharge is defined as the subject leaving the treating or referral hospital. The discharge will be performed per the site's SOC.

All subjects registered for the clinical study will have follow-up assessments, with either a clinic visit at the investigational center or a telephone contact at the time points listed below.

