#### **6.4.1 Follow-up for All Subjects**

Subjects registered in the clinical study will receive the following clinical follow-ups from the index procedure date (day 0):

- 1 month ( $30 \pm 7$  days)
- 6 months ( $180 \pm 14$  days)
- 12 months ( $365 \pm 28$  days)
- 24 months ( $730 \pm 28$  days)
- 36 months ( $1095 \pm 28$  days)

For all follow-ups, either clinic visits or phone visits are allowed. To aid in follow-up compliance, if necessary, an independent service may be utilized to provide in-home visits for clinical follow-up.

Clinical follow-up visits should be conducted by the investigator or trial personnel who have been trained to the protocol.

The following information will be collected at each of the time points:

- Any adverse events
- Antiplatelet medication
- Details of any subsequent coronary interventions (e.g., repeat PCI or coronary artery bypass graft [CABG])

Note that information obtained through indirect contact with a subject's healthcare provider or immediate family member will NOT be considered a trial visit, except when a subject passes away. Additional information for a visit, if needed but missed, may be obtained by reaching out to the subject after the visit to ensure complete data collection.

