#### 6.4.4 Schedule of Events

PROCEDURE/TEST	Baseline/pre-procedure (within 3-months prior to index procedure)	Procedure	Post-Procedure	1-month (30±7d) Clinic visit or phone contact 	6-month (180 ±14d) Clinic visit or phone contact 	12-month (365 ± 28d) Clinic visit or phone contact 	24-month (730 ± 28d) Clinic visit or phone contact 	36-month (1095 ± 28d) Clinic visit or phone contact 	Unscheduled visits
Subject Medical/Clinical History	✓								
Subject Informed Consent	✓		✓						
General Inclusion/Exclusion Criteria	✓								
ECG	✓ 		✓ 						
Angiographic Inclusion/Exclusion Criteria including SYNTAX score if LMCA is treated		✓							
Coronary Angiogram		✓							✓
cTn biomarker measurement(s)	✓ 		✓ 						
Stent and Procedure Information		✓							
Post-procedure Antiplatelet Medications			✓	✓	✓	✓	✓	✓	✓
Adverse Events		✓	✓	✓	✓	✓	✓	✓	✓

 For all follow-up visits, either clinic visits or phone visits are allowed. To aid in follow-up compliance, if necessary, an independent service may be utilized to provide in-home visits for clinical follow-up.

 Pre-procedure ECG is highly recommended, post-procedure ECG is mandatory.

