## **7.2 Adverse Event and Device Deficiency/Device Malfunction Reporting**

### **7.2.1 Adverse Event Reporting**

#### General AE Reporting

Safety surveillance and reporting start as soon as the subject is registered in the clinical study. Safety surveillance and reporting will continue until the last follow-up visit has been performed, the subject is deceased, the subject concludes participation in the clinical study, or the subject withdraws from the clinical study. For the purposes of this clinical study, the following events will be reported to the Sponsor on a CRF: device- and procedure-related AEs, SAEs, cardiovascular-related AEs, deaths and device deficiency data. Additional information with regard to an AE should be updated within the appropriate CRF. AEs will not be collected for screen failure subjects. If the subject gets consented after the index procedure, reporting will be collected from the index procedure, and the AE awareness date should be entered the same as the post-procedure consent date.

Unchanged, chronic, non-worsening or pre-existing conditions are not AEs and should not be reported. The Sponsor will provide an offline form to allow the investigator to report SAEs if the entry cannot be made in the electronic data capture (EDC). This does not replace the EDC reporting system. Sites must still enter all information in the EDC system as soon as feasible.

Non-cardiac related abnormal laboratory values will not be considered AEs unless:

1. the investigator determined that the value is clinically significant,
2. the abnormal lab value required intervention, or
3. the abnormal lab value required subject withdrawal from the clinical study.

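### Consent may be taken after the procedure, up to discharge, while TLF runs from the procedure; without consecutive approach or an implant log, early deaths and selective approach on that route go unrecorded

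*Protocol*

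**What the plan says.** **Timing of consent.** Protocol section 5.2.2 states that an informed consent form "must be obtained from a subject who is willing to participate in the SPIRIT XLV PAS study prior to discharge". Section 6.4 sets the outer limit: "Discharge is defined as the subject leaving the treating or referral hospital". In the schedule of events (6.4.4) the row "Subject Informed Consent" is ticked in both the pre-procedure and the post-procedure column. Section 7.2.1 plans for the late case: "If the subject gets consented after the index procedure, reporting will be collected from the index procedure".

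**Limit on late consent.** Section 5.2.2 also requires consent before any study-specific procedure that is not the site's standard of care, and gives cardiac biomarkers before and after the procedure, and the SYNTAX score for left main targets, as possible examples. Section 6.1.2 makes a baseline troponin mandatory and has it drawn before any angioplasty. Section 5.3.1.1 allows a legally authorized representative to consent.

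**Start of enrolment and of follow-up.** Section 5.4: "A subject is considered to be enrolled in the study from the moment the subject provides written informed consent". Section 6.4.1 counts all follow-up from the index procedure as day 0.

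**Endpoint.** Section 4.1: "The descriptive primary endpoint is Target Lesion Failure (TLF) at 1 year". Its components are cardiac death, target-vessel MI and ischemia-driven TLR. Appendix II counts procedure-related deaths as cardiac and defines periprocedural MI within 48 hours of the procedure.

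**Protection against bias.** Section 3.2: "A Clinical Events Committee (CEC) and an angiographic core laboratory will be utilized on this study to avoid and minimize bias".

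**The concern.** On the late route, entry to the study comes after the start of the period in which events are counted. Two things follow.

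- The patient must be alive when consent is given. A cardiac death between procedure and consent is a primary endpoint event in a treated patient, but that patient is in neither the numerator nor the denominator.
- The person choosing whom to approach can already know the angiographic result, the early clinical course and possibly the troponin. Nothing visible obliges the site to ask every eligible recipient.

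The study has one arm and its primary endpoint is descriptive, so the 1-year TLF rate is itself the main result and no concurrent arm shares the distortion. Losing patients with early events always moves the rate down, which favours the device.

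**Working it through.** **Step 1: can the late route lose events when the plan is followed exactly?** Set the provisions side by side.

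- Consent is acceptable until discharge (5.2.2, 6.4, 6.4.4).
- Enrolment exists only from written consent (5.4).
- Follow-up starts at the procedure (6.4.1), and events are collected back to it for those who consent late (7.2.1).
- Fatal and non-fatal TLF events can occur within hours of the procedure (Appendix II).

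A patient not consented beforehand who dies before anyone consents therefore drops out with no deviation from the protocol. Back-collection restores early events only in patients who go on to consent. It does not change who consents.

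**Step 2: who is exposed?**

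- *Consented before the procedure:* not exposed. Such a subject who is implanted, confirmed eligible and then dies is registered and counted.
- *Site where baseline troponin is not standard of care:* consent must precede the draw, which precedes angioplasty, so late consent is closed. The secondary-endpoint text in Appendix X shows that a site without troponin as standard of care exists.
- *Site where the study tests are standard of care:* late consent is open.
- *Incapacitated patients:* a representative may consent. The text does not extend this to patients who have died.

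**Step 3: do the existing safeguards reach selection?** The CEC adjudicates events and the core lab reads images. Both work on subjects already in the study. The visible recruitment, consent and registration text (5.2.1, 5.2.2, 5.4) requires neither consecutive approach nor a list of implanted patients who were not enrolled.

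**Step 4: size, as illustration only.** The visible protocol gives no expected TLF rate and no share of late consent, so there is no plan figure to reproduce. Every input below is an assumption:

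- true 1-year TLF *p* = 6%
- in-hospital cardiac death *d* = 1%, all taken to fall before consent on the late route
- share approached only after the procedure *f* = 30%, 60% or 90%

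If only these deaths are lost:

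observed TLF = (*p* − *f·d*) / (1 − *f·d*)

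| *f* | Calculation | Observed TLF | Shortfall (points) |
|---|---|---|---|
| 30% | (0.060 − 0.003) / 0.997 | 5.72% | 0.28 |
| 60% | (0.060 − 0.006) / 0.994 | 5.43% | 0.57 |
| 90% | (0.060 − 0.009) / 0.991 | 5.15% | 0.85 |

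If some in-hospital deaths come after consent, they are counted and the shortfall is smaller. If sites also pass over patients with early non-fatal events, it is larger. Suppose a further 2% have an in-hospital non-fatal TLF event and half of those on the late route are not enrolled. The loss becomes *f* × (1% + 1%), and the observed rate is 0.054/0.994 = 5.43% at *f* = 30% and 0.042/0.982 = 4.28% at *f* = 90%. The documents offer no evidence that sites would do this.

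**The case against.** The strongest case against runs as follows.

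- **Late consent is reasonable here.** Eligibility depends on an angiographic vessel diameter and on actually receiving a study-size stent, and acute MI patients are eligible. Many candidates may be recognisable only at the procedure. This stands, and it is why the route should be kept.
- **Exposure is limited.** Pre-procedure consent, consent by a representative and the standard-of-care rule all narrow it. This stands. A reader might infer that early deaths can never enter this study. The documents do not support that, because it holds only for patients whose consent was not obtained beforehand.
- **A safeguard may exist out of sight.** Section 5.6 is blank, sections 8.1 to 8.5 and the endpoint footnote are redacted, and the SAP is not at hand. This stands as a limit on what can be claimed. A reader might infer that nothing in the plan would let the bias be seen, and the visible text cannot establish that. But consecutive approach and an implant log are rules for site conduct. No later analysis can recover patients whom nobody recorded.
- **The figures are assumed and the endpoint is descriptive.** This stands. No visible hypothesis or performance goal would be overturned by a shift of this size.
- **One secondary endpoint is less exposed.** The version of TLF that excludes periprocedural MI is less open to selection on that event. It still misses deaths before consent.

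**Conclusion.** The point holds for the post-procedure consent route. Followed exactly, the plan lets deaths before consent go uncounted and lets sites choose whom to approach knowing the acute result, while the only bias measures named in section 3.2 act after selection. The direction is certain when early-event patients are lost: the 1-year TLF is too low.

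The size is unknown. Under the assumptions in the working, losing deaths alone takes a true 6% to between 5.7% and 5.2%. These figures show scale and do not estimate this study's bias. The lower figure of 4.3% needs both 90% late consent and non-enrolment of half of the early non-fatal cases, and should not be read as an expected result.

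This is a cheap improvement to conduct and reporting. It is not a defect that invalidates the design.

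**What to change.** Keep post-procedure consent and add the following to section 5.2.

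1. **Consecutive approach.** Sites approach every eligible recipient of a 4.5 or 5.0 mm study stent in consecutive order during enrolment.
2. **Minimal anonymous log.** Sites record every such implant during enrolment: consented or not, consent before or after the procedure, and in-hospital death where the IRB/EC permits. Record before or after explicitly, because the dated signature alone does not order consent and procedure on the same day.

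In the report, give the number of recipients not enrolled and their in-hospital deaths beside the primary result. Tabulate TLF by consent timing as a descriptive check. Timing is confounded by clinical presentation and site practice, so a difference would not isolate selection and similar rates would not prove its absence. Do not substitute a landmark analysis from consent for the primary estimate: it drops events before consent, including periprocedural MI, and so answers a different question.

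The cost is modest site effort for a one-line log entry per implant, possibly IRB/EC agreement for the log, and an extra table.
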